Objectives	The primary objective of this study is to show that, when used before, during, and after an EP procedure, CoVa™ 2 is able to successfully measure vital signs, waveforms, and hemodynamic parameters from patients, indicate the efficacy of the EP procedure, and show any signs of patient decompensation or complications. An additional objective of this study is to show that, through use of CoVa™ 2, patients can be discharged relatively early from the hospital after undergoing an EP procedure.
Methodology	No randomization or blinding methods will be used for this study.
Endpoint	The primary endpoint will be if at least 50% of subjects studied in this trial are able to be discharged relatively early from the hospital if they are monitored with CoVa™ 2. A detailed retrospective statistical report will be the determining factor in meeting this success criteria.
Study Duration	Approximately 6 months
Participant Duration	Up to 7 days (until hospital discharge).
Duration of IP administration	N/A
Population	Approximate sample size: 20 subjects. Subjects are those which need an EP procedure,, including atrial fibrillation and SVT, pacemaker or ICD implant.
Study Sites	NYU Medical Center Electrophysiology [name]
Number of participants	20 subjects across one site

Description of Study Agent/Procedure	Subjects will be measured with CoVa™ 2 before and after an EP procedure.
Reference Therapy	N/A
Key Procedures	EP
Statistical Analysis	Statistical comparison (e.g. correlations) of measurements made before, during, and after the EP procedure to prove or disprove the above-mentioned study hypothesis.

Schematic of Study Design

1 Key Roles

Principle Investigator
[name]
[contact]

Sub Investigator
[name]
[contact]

Introduction, Background Information and Scientific Rationale

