Once the EP procedure is complete, the subject will be transferred from the operating room to a hospital room, where they will stay overnight. Measurements will be made during this period, but not while the subject is being transferred. Once the subject is situated in the hospital room, the CoVa™ 2 Sensor will be applied to the subject and connected to the external power supply in the same manner as described above. Then measurements will commence according to the same duty cycle as described above.

The patient will continuously wear the CoVa™ 2 system until they are discharged for a period of about 24 hours. During this period, data from the sensor will be sent to the Gateway and Cloud-based System, and then analyzed retrospectively.

During the course of the study, scientists at toSense will use the Data Analytics Software to process measurement information from CoVa™ 2, with a focus of proving or disproving the study's primary hypothesis, i.e. when the CoVa™ 2 Sensor is used before, during, and after an EP procedure, can it successfully measure patients, indicate the efficacy of the EP procedure, show any signs of patient decompensation or complications, and allow a patient to be discharged relatively early?

More detailed analyses will investigate the study's secondary objectives, i.e.: 1) can measurements made by the CoVa™ 2 Sensor be successfully made before, during, and after an EP procedure; 2) is there correlation between parameters such as volume status, heart rate and arrhythmia, SV, and CO before, during, and after an EP procedure; 3) does RF ablation during an EP procedure interfere with CoVa™ 2 Sensor measurements?; 4) does a shock during a DC cardioversion interfere with CoVa™ 2 Sensor measurements?; and 5) is the usability of the CoVa™ 2 Sensor adequate before, during, and after an EP procedure suitable for clinicians?

Upon completion of the study, a report will be drafted describing the above-described information. The report may evolve into a peer-reviewed publication if this is determined by the PI to be an appropriate course of action.

This measurement protocol will be performed for a period of at approximately 6 months.

Study Endpoints

Primary Study Endpoints

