The primary endpoint will be if at least 50% of subjects studied in this trial are able to be discharged relatively early from the hospital if they are monitored with CoVa™ 2, as determined through a retrospective analysis. A detailed retrospective statistical report will be the determining factor in meeting this success criteria.

Study Enrollment and Withdrawal

Inclusion Criteria

In order to be eligible to participate in this study, an individual must meet all of the following criteria:

1. Patients with arrhythmias and other cardiac conditions that are scheduled for EP procedures.
2. Subject is over 22 years of age at the time of consenting
3. Subject and/or legally authorized representative is willing to undergo the informed consent process prior to enrollment in the study

Exclusion Criteria

An individual who meets any of the following criteria will be excluded from participation in this study:

1. Pregnant subjects
2. Subjects who are participating in another clinical study that may affect the results of either study

3. Subjects who are unwilling or unable to wear the sensor (and electrodes) for a period of up to 14 hours
4. Subjects who are considered by the principle investigator to be medically unsuitable for study participation

Vulnerable Subjects

Vulnerable subjects will not be utilized in this study. In the case of a vulnerable population patient being identified; they will not be included in the study or analysis..

Strategies for Recruitment and Retention

No NYULMC media will be used to recruit subjects. Subjects that are scheduled for an EP procedure and meet the inclusion criteria will be approached for enrollment.

Subjects will be consented in a quiet and private environment. Subjects will be given the opportunity to take the written consent form home to review overnight.

Use of DataCore/Epic Information for Recruitment Purposes

This study will utilize EPIC to identify subjects. Once potential subjects have been identified, the study team will notify the treating physician (TP) that they have patients eligible to participate. The study team will obtain approval from the treating physician to approach the eligible patient for the study.

Duration of Study Participation

The total duration of study participation is about 1.5 days. This includes:

Written Informed Consent Process: 1 day

Study Procedure: 1 day

Measurement prior to EP Procedure: 1-3 hours

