Measurement after EP procedure: Patient will be measured until they are discharged from hospital (approximately 24 hours).

Subjects may be contacted for a follow-up interview.

Total Number of Participants and Sites

This is a single-site study. Recruitment will end when approximately 20 participants are enrolled. It is expected that approximately 20-30 participants will be recruited in order to produce 20 evaluable participants.

Reasons for Withdrawal or Termination

Participants are free to withdraw from participation in the study at any time upon request. An investigator may terminate participation in the study if:

- Any clinical adverse event (AE), laboratory abnormality, or other medical condition or situation occurs such that continued participation in the study would not be in the best interest of the participant
- The participant meets an exclusion criterion (either newly developed or not previously recognized) that precludes further study participation

Handling of Participant Withdrawals or Termination

Withdraw criteria:

- The Principle Investigator will review whether a withdrawal of a subject affects the success criteria of the study. A subject may be replaced if it is determined that more subjects are needed based on this criterion

Premature Termination or Suspension of Study

This study may be temporarily suspended or prematurely terminated if there is sufficient reasonable cause. Written notification, documenting the reason for study suspension or termination. If the study is prematurely terminated or suspended, the PI will promptly inform the IRB and will provide the reason(s) for the termination or suspension.

Circumstances that may warrant termination or suspension include, but are not limited to:

- Determination of unexpected, significant, or unacceptable risk to participants
- Demonstration of efficacy that would warrant stopping
- Insufficient compliance to protocol requirements
- Data that are not sufficiently complete and/or evaluable
- Determination of futility

Study may resume once concerns about safety, protocol compliance, data quality are addressed and satisfy the IRB.

Study Agent (Study drug, device, biologic, vaccine etc.) and/or Procedural Intervention

Study Agent(s) and Control Description

Acquisition

toSense will ship CoVa™ 2 systems directly to the Electrophysiology supplies team at the NYU medical center.

New York Medical Center
[name],
[name]
New York, NY
10016

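### Replacement of withdrawn subjects is tied to the success criteria rather than to a result-free count, so the expected result could influence who is replaced

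*Protocol*

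**What the plan says.** Protocol, Handling of Participant Withdrawals or Termination: "The Principle Investigator will review whether a withdrawal of a subject affects the success criteria of the study". The next sentence gives the consequence: "A subject may be replaced if it is determined that more subjects are needed based on this criterion".

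The term success criteria is used otherwise only for the primary endpoint, in Primary Study Endpoints and in the Endpoint row of the Protocol Summary: "The primary endpoint will be if at least 50% of subjects studied in this trial are able to be discharged relatively early", followed by "A detailed retrospective statistical report will be the determining factor in meeting this success criteria".

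Other places that bear on the rule:

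- Protocol Summary, Methodology: "No randomization or blinding methods will be used for this study".
- Description of Study Design: "During the course of the study, scientists at toSense will use the Data Analytics Software to process measurement information". The stated focus of that work is the primary hypothesis, which includes early discharge.
- Total Number of Participants and Sites: "Recruitment will end when approximately 20 participants are enrolled", and then an expectation that "approximately 20-30 participants will be recruited in order to produce 20 evaluable participants".
- Withdrawal/Early Termination Visit: replacement is allowed again, this time with no criterion. The same list asks staff to try to learn the reason and to record whether the subject or the investigator initiated the withdrawal.

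**The concern.** A replacement rule should depend on something fixed before results are known, usually a count of evaluable subjects. Here the deciding question is whether the withdrawal affects the success criteria, and in this protocol that phrase means the pass/fail proportion. Read literally, the investigator is asked to consider the likely result before deciding whether to add a subject.

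Nothing in the protocol keeps the investigator unaware of results, and device data are processed while the study runs. Withdrawal can also be related to outcome: under Reasons for Withdrawal or Termination, an investigator may end participation for an adverse event or other medical condition, which may also bear on early discharge.

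Because success is a bare proportion in about 20 subjects, a narrow pass that followed a replacement could be challenged from the protocol's own words. The group being counted is also unsettled: the protocol speaks of subjects enrolled, recruited, evaluable and studied without linking these terms.

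**Working it through.** **Inputs.** From the protocol: 20 evaluable subjects, 20 to 30 recruited, success at 50% or more, so at least 10 of 20. Not in the protocol, and assumed here: a true early-discharge rate p = 40% and a withdrawal rate w = 10% or 20%.

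**The plan's own figure.** The 20 comes with no alpha, power or assumed rate, so it cannot be reproduced. The recruitment range is consistent with 20/(1 − d): d = 0 gives 20 and d = 1/3 gives 30.

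**1. Fixed 20 subjects.** With X ~ Bin(20, 0.40), P(X ≥ 10) = 24.5% and P(X = 9) = 16.0%.

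**2. One subject at the margin.** 9/20 = 45% fails. Dropping one failure gives 9/19 = 47.4%, which still fails. Replacing that failure by a success gives 10/20 = 50%, which passes. If one known, withdrawn failure were always available and were replaced only when the count fell short, the chance of passing would be P(X ≥ 10) + p × P(X = 9) = 0.2447 + 0.40 × 0.1597 = 30.9%. At other assumed true rates the change is 4.8% to 6.8% (p = 30%), 40.9% to 48.8% (45%) and 58.8% to 66.8% (50%). These figures are conditional on such a subject existing; they are not expected effects.

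**3. Neutral top-up.** Withdrawal is unrelated to outcome and replacement continues to 20 evaluable, with at most 30 recruited. In 200,000 simulated trials the pass rate is 24.4% (w = 10%) and 24.3% (w = 20%). There is no inflation.

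**4. Only withdrawn failures replaced.** The success rate per slot becomes p/(1 − w(1 − p)).

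- w = 10%: 0.40/0.94 = 0.4255, and P(X ≥ 10) = 32.5%.
- w = 20%: 0.40/0.88 = 0.4545, and P(X ≥ 10) = 42.5%.

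**5. The same withdrawals with no replacement.** Of 20 enrolled, each subject is a success (0.40), a retained failure (0.60 × (1 − w) = 0.54 or 0.48) or a dropped failure (0.06 or 0.12). The trial passes if successes are at least as many as retained failures. Summing the trinomial gives 29.8% or 39.5%.

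| | w = 10% | w = 20% |
|---|---|---|
| Fixed 20, all counted | 24.5% | 24.5% |
| Withdrawn failures dropped, not replaced | 29.8% | 39.5% |
| Withdrawn failures dropped and replaced | 32.5% | 42.5% |
| Rise due to the denominator (points) | 5.3 | 15.0 |
| Rise due to replacement (points) | 2.7 | 3.0 |

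**6. Replacement blind to outcome, failures twice as likely to withdraw.** Withdrawal among successes is w/(0.40 + 2 × 0.60) = 6.25% or 12.5%, and among failures 12.5% or 25%. The success rate among those remaining is 0.40 × 0.9375/0.90 = 0.4167 or 0.40 × 0.875/0.80 = 0.4375. The pass rate is 29.6% or 36.5% with replacement, and 27.5% or 35.2% without. Again most of the rise does not come from replacement.

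**The case against.** The strongest reply is that the rule asks whether more subjects are needed, which is a question of number, and that the same part of the protocol supplies a neutral number: 20 evaluable. Top-up to that number fits both statements and, by step 3, does no harm when withdrawal is unrelated to outcome. This reading is plausible. What stands against it is that the rule names the success criteria as its test and does not mention the evaluable target.

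A second reply is that the route to bias is indirect. Success is determined retrospectively, and no section gives the investigator per-subject discharge results when a withdrawal is reviewed. Access rules may also sit in documents not shown, and a subject who leaves before discharge may have no determinable outcome. This lowers the risk but does not remove the instruction. A statistical analysis plan could define the analysis set and still leave this conduct rule in force.

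A third reply, that most of the quoted inflation belongs to the denominator, is correct by steps 5 and 6. How withdrawn subjects count is commonly left to the statistical analysis plan and is not held against this protocol.

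A reader might also infer that the rule allows subjects to be withdrawn because of their result. It does not: it governs only replacement, and the listed grounds for withdrawal are the participant's request, a medical or safety reason, or an exclusion criterion.

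**Conclusion.** The concern holds in a limited form. The replacement rule is badly fixed: its literal test is the trial's own pass/fail criterion, applied at the investigator's discretion in an unblinded study where one subject can decide the result.

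The documents do not support saying that replacement will be driven by results, or that the full rise to 32.5% or 42.5% is the effect of replacement. Under the assumed 40% true rate and 10% or 20% withdrawals, replacement accounts for about 3 points of that rise, and for none under a neutral top-up with withdrawal unrelated to outcome. Both rates are assumptions, because the protocol gives neither.

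Severity is minor to moderate: this is an introductory single-arm study with no stated hypothesis test, and the correction is cheap and right under either reading of the rule.

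**What to change.** (a) Reword the two sentences in Handling of Participant Withdrawals or Termination along these lines: a withdrawn subject who is not evaluable, by a definition set in advance and unrelated to outcome, may be replaced until 20 evaluable subjects are reached; the decision is made without reference to the success criteria or to any results. Have Withdrawal/Early Termination Visit refer to this rule.

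(b) In Total Number of Participants and Sites, reconcile the stop at about 20 enrolled with 20 evaluable out of 20 to 30 recruited. Use the same term in the primary endpoint, in place of subjects studied.

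(c) Optionally, report the 50% criterion also with every withdrawn subject, including those replaced, counted as not meeting it. Rewording alone does not remove bias when failures are more likely to withdraw (step 6), and this figure shows how far the result depends on withdrawals.

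Cost: (a) and (b) are wording only; (c) is one more proportion, and a less favourable one. With top-up to 20 evaluable, at most 30 recruited, and withdrawal unrelated to outcome, that proportion reaches 50% in about 11% (10% withdrawals) or 5% (20%) of simulated trials at a true rate of 40%, against 24.5% for the primary count. At a true rate of 60% it does so in about 69% or 47%, against 87%. It should therefore stay a conservative sensitivity figure and not replace the primary result.

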In addition to the primary study objective, investigate the following questions: 1) can measurements made by the CoVa™ 2 (particularly stroke volume (SV), cardiac output (CO), fluid status, arrhythmia detection, and basic vital signs) be successfully made before, during, and after an EP procedure?; 2) is there correlation between CoVa™ 2-measured parameters (particularly volume status, heart rate and arrhythmia, SV, and CO) before, during, and after an EP procedure?; 3) does RF ablation during an EP procedure interfere with CoVa™ 2 measurements?; 4) does a 200-300 Joule shock during a DC cardioversion procedure interfere with CoVa™ 2 measurements?; and 5) is the CoVa™ 2's usability suitable for hospital clinicians?

Description of Study Design

Study subjects scheduled for an EP procedure who have signed an informed consent form (ICF) will be admitted to the study. Prior to the EP procedure (e.g. in a hospital room or operating room at NYU Medical Center), an employee of NYU will prep the subject's skin with an alcohol wipe, apply the CoVa™ 2 Sensor using a pair of disposable electrodes, connect it to the Gateway Device using Bluetooth®, and ensure that it is transmitting information from the CoVa™ 2 Sensor through the Gateway Device to the Cloud-based System. All transmitted information will be de-identified. All subjects will continue to be monitored with standard of care equipment.

Once this data pathway is verified, measurements will be made from the subject for a period of approximately 2 hours prior to the EP procedure. More specifically, measurements will be made continuously for a period of about 90 seconds, and then, as described above, information will be transferred from the CoVa™ 2 to the Gateway Device, and from the Gateway Device to the Cloud-based System. This process will take roughly 120 seconds. Once it is complete, this 'duty cycle' will be repeated for the duration of the 2-hour period, i.e. measurements will again commence for a period of about 90 seconds, and then paused for about 120 seconds while data is wirelessly transmitted as described above.

Measurements will be temporarily halted as the subject is moved into the operating room and prepped for the EP procedure. Prior to the procedure, the CoVa™ 2 sensor will be attached to an external power supply as described above. Once the procedure is started, measurements will be made in the same manner as described above.

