Devices will only be shipped once. The sensors should be kept as instructed in the product and stability section of this protocol.

Formulation, Appearance, Packaging, and Labeling

Devices are labeled with the follow symbols:

	Keep Dry
	Type BF – applied part
	Non-defibrillation proof device
	FCC certified
	Read Usage Instructions
	Single Use Only
	Necklace is MR Unsafe. Necklace should not be worn during MR Scan
	Wireless Transmission

Each device is labeled with a unique identifier (UID). The proposed product is available to human use in its current form.

Product Storage and Stability

Environmental Conditions for the CoVa™ Monitoring System 2		
Condition	Storage (Packaged / Unpackaged)	Operating (Unpackaged)
Temperature	-25°C to +70°C -13°F to +158°F	-5°C to +50°C 22°F to +122°F
Humidity	up to 93% non-condensing	10% to 93% non-condensing
Atmospheric Pressure Range	700 hPa to 1060 hPa	700 hPa to 1060 hPa
Shelf Life	Necklace: 6 months Electrodes: 2 years	Necklace: 6 months Electrodes: 24 hours

Device Specific Considerations

Physical Characteristics:

- Dimensions: 1cm H x 18.0 cm W x 30 cm L (0.4 in H x 6.5 in W x 13 in L)
- Weight: 0.127 kg (4.5 oz)
- Battery Type: Li-ion

Administration of Intervention

Devices will be placed on consented subjects either directly by the PI or qualified research staff.

Procedures for Training Interventionalists and Monitoring Intervention Fidelity

toSense will provide CoVa™ 2 on-site training to the PI, study staff and Co-Investigators.

Study Procedures and Schedule

Study Specific Procedures

CoVa™ 2 systems will be set up and attached to patients according to procedures described in toSense's FDA-cleared documentation.

Screening

The study team will screen for eligible patients using EPIC. Approval to approach eligible patients will be obtained from the TP. No research related activities will be conducted until eligible patient's have signed the consent form.

Enrollment/Baseline

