The PI will confirm prior to enrollment that each subject qualifies for the study. The eligible subject will be approached by the research team. All patients willing to participate will personally sign and date the latest IRB approved version of the consent form. Written and verbal versions of the participant information and informed consent will be presented to the participants detailing no less than: the exact nature of the study; the implications and constraints of the protocol; the known side effects and any risks involved in taking part. It will be clearly stated that the participant is free to withdraw from the study at any time for any reason without prejudice to future care, and with no obligation to give the reason for withdrawal. The participant will be allowed as much time as wished to consider the information, and the opportunity to question the Investigator, their general practitioner or other independent parties to decide whether they will participate in the study. Written Informed Consent will then be obtained by means of participant dated signature and dated signature of the person who presented and obtained the informed consent. A copy of the signed Informed Consent will be given to the participants. The original signed form will be retained at the study site, in a research binder maintained by the study team in a locked cabinet. All documents will be stored safely in confidential conditions. On all physical and electronic study-specific documents, other than the signed consent, the participant will be referred to by a study participant number/code, not by name.

Visit 2 (Day of EP procedure)

- Ensure the subject has no additional questions regarding the study
- Once the subject has been prepped for surgery, apply the sensor to the subject's upper chest using the toSense approved electrodes
- Connect the device to the power source
- Study participant will be assigned a study number/code

- All data transmitted by the CoVa2 device will be de-identified.
- Run several test measurements on the sensor to ensure that the device is actively measuring on the subject
- Explain to the subject that the sensor will measure for a 90 seconds period, with 120 second pause in between measurements
- Measurements will not be made while the subject is transferred to and from the surgery room
- Measurements will be made until the patient is discharged

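### Secondary objective 4 studies cardioversion shocks with a sensor labelled as not defibrillation proof, and the protocol neither reconciles the two nor says how the sensor is handled at a shock

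*Protocol*

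**What the plan says.** **The objective.** Secondary Objectives asks "does a 200-300 Joule shock during a DC cardioversion procedure interfere with CoVa™ 2 measurements". Description of Study Design repeats it among the detailed analyses: "does a shock during a DC cardioversion interfere with CoVa™ 2 Sensor measurements".

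**Where the sensor is.** Under Visit 2, staff are to "apply the sensor to the subject's upper chest using the toSense approved electrodes" and then "Connect the device to the power source". Description of Study Design says "Prior to the procedure, the CoVa™ 2 sensor will be attached to an external power supply as described above", followed by "Once the procedure is started, measurements will be made in the same manner as described above".

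**When measurement stops.** Apart from the pauses of the duty cycle, the stated halts are for transfer and preparation: "Measurements will be temporarily halted as the subject is moved into the operating room and prepped for the EP procedure", with a matching halt on the way back. The only explicit removal step is just before discharge.

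**The label.** Formulation, Appearance, Packaging, and Labeling lists the entry "Non-defibrillation proof device" without explanation.

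**The risks.** Known Potential Risks covers skin redness or irritation, reaction to the adhesive, and discomfort when patches are removed. Shocks do not appear. No exclusion criterion refers to planned cardioversion.

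**The concern.** One part of the protocol makes a high-energy shock an exposure to be studied. Another lists the device, without comment, as not proof against defibrillation. Staff following the plan would probably have the sensor on a subject's chest when the shock is delivered, with no instruction to remove it, disconnect it or check it afterwards.

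What is at stake depends on what the entry means:

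- If it concerns the patient, there is a gap in the protocol's safety provisions and risk section.
- If it concerns only the device, a damaged sensor could distort the answer to objective 4. It could also distort that subject's later recordings, which are part of the data analysed retrospectively for early discharge.

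**Working it through.** The plan gives no figure to reproduce, so the check compares sections.

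1. **Is a shock within the study's scope?** Yes. Objective 4 names the energy range, 200 to 300 J, and Description of Study Design carries the question into the planned analyses.
2. **Is the sensor on and measuring during the procedure?** By implication, yes. It is placed on the upper chest, connected to power, and measures once the procedure starts. No sentence says that it stays on through a shock.
3. **Does any step take it off or disconnect it for a shock?** None is stated. Description of Study Design has the sensor applied once the subject is settled in the hospital room, so it presumably comes off at some point around transfer. Nothing ties that removal to a shock.
4. **Does the label entry carry an instruction?** No. The MR entry in the same list says that the necklace is not to be worn during a scan. The defibrillation entry says nothing about wear, so it neither forbids nor supports it.
5. **Is the conflict resolved elsewhere?** Not in the text shown. Study Specific Procedures refers to the manufacturer's cleared documentation for set-up and attachment. The label list tells users to read the instructions, on-site training is promised, and the consent process is to cover risks in general. None of these mentions shocks.
6. **How many subjects are affected?** The population includes atrial fibrillation, SVT, and pacemaker or ICD implant, with no count of expected cardioversions. Recruitment is 20 to 30 to give 20 evaluable subjects. Exposure therefore lies between 0 and all of the 20 to 30 recruited.

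**A side point on interpreting objective 4.** The sensor measures for about 90 s and pauses for about 120 s. If the timing of a shock is unrelated to the cycle, the expected share of shocks falling while the sensor is measuring is 90/(90 + 120) = 90/210 = 43%. Both times are approximate. Assuming each may be off by 15 s in opposite directions, the range is 75/(75 + 135) = 36% to 105/(105 + 105) = 50%. So even with the sensor worn, roughly half or more of the shocks would fall in a pause and say nothing direct about transient interference. The label conflict does not depend on this.

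**The case against.** The strongest reply is that the hazard rests on documents nobody here has seen. The label entry is not explained, and the list shows that it can state a ban when one is meant, as it does for MR. The manufacturer's documentation, the training, the consent form or the attachments cited for clinical data may deal with shocks. Cardioversion appears as part of the patient's own care, not as something the study imposes, so only an added risk from the device would belong under Known Potential Risks. The investigator can also exclude unsuitable patients or end participation in the subject's interest.

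Much of this stands, and it rules out several stronger readings that a reader might infer:

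- **That the label prohibits wear during a shock.** The text shown does not say so.
- **That the protocol orders wear through a shock.** This is an inference, though a natural one. The Description of Study Agent/Procedure row of the Protocol Summary even speaks of measuring only before and after the procedure, although other sections include the time during it.
- **That the external supply adds an electrical danger.** The supply is said to be described above, but no earlier text describes it, so no added hazard can be shown.
- **That objective 4 cannot be answered unless the sensor stays on.** A comparison before the shock and after re-application remains possible, although it answers a narrower question.
- **That subjects are not told of the risk.** The consent form is not shown. The omission is established only for the protocol's own risk section.

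What the reply does not remove is the conflict itself. General references to set-up documents, training and investigator discretion do not tell staff what to do with this sensor at a shock that the protocol sets out to study. Handling steps and risk disclosure are protocol content and would not normally be left to a statistical analysis plan.

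**Conclusion.** The point holds as an unreconciled conflict that should be fixed before the first shock with the sensor on. The protocol studies 200 to 300 J shocks, implies that the sensor is on the chest and measuring, lists the device as not defibrillation proof, gives no shock-specific handling step, and omits shocks from its risk section.

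Its size is open: 0 up to all of the 20 to 30 recruited, with an unknown consequence for each subject shocked. Neither a patient hazard nor an effect on the primary endpoint is shown. The conclusion assumes that the steps in Description of Study Design and Visit 2 are followed as written, and that no document outside those shown already settles the matter. Confidence is medium for those reasons.

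**What to change.** Ask the manufacturer for its written position on the label entry, and amend Visit 2 accordingly.

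- **Unless wear through a shock is confirmed as acceptable:** remove the sensor and disconnect it from external power before any cardioversion, never delaying an emergency shock. Limit objective 4 to measurements before the shock against those after re-application.
- **If wear is confirmed as acceptable:** add any device-related shock risk to Known Potential Risks and to the consent form. Add a device check after each shock, to be passed before later recordings from that subject are used.
- **Optional, if the sensor is worn:** log the clock time of each shock, report how many fell inside a measurement window, and confine claims about transient interference to those. Do not time shocks to fit the cycle.

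**Cost.** One query to the manufacturer, a short amendment for IRB review and some staff time. With removal there is also a gap in sensor data around the shock, while standard-of-care monitoring continues, and objective 4 becomes narrower.
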